4.2 STATISTICAL METHODS

Tabulation of summary statistics, graphical presentations, and statistical analyses will be performed using SAS® software 9.1.3 or higher version. Where not otherwise specified, the last pre-treatment observation will be used as baseline for calculating post-treatment changes from baseline. The primary presentations and analyses will be based on data pooled across study centers. Relevant summaries for individual centers, or combinations of centers, may be presented for primary data. All testing and confidence intervals will use a significance level of 5%.

4.3 DEMOGRAPHIC AND BASELINE CHARACTERISTICS

All demographic and baseline characteristics will be tabulated by treatment group and a test of homogeneity between the treatment groups will be conducted. For continuous variables (e.g. age, height, weight) a one way ANOVA will be used. For categorical variables (e.g. gender, race), a Fisher's exact test or chi-squared test will be used. Medical history findings, physical examinations and concomitant medications will be tabulated by treatment group.

The baseline Chemistry, Hematology, Urinalysis, Vital Signs, and BMI data will be summarized via descriptive statistics and tested for homogeneity using a one way ANOVA.

4.4 ADVERSE EVENTS

All AEs will be coded according to MedDRA. Safety assessments will include Treatment-Emergent Adverse Events (TEAEs) which are defined as AEs with an Investigator assessment of definitely, probably, or possibly related to CTM. TEAEs will be summarized with frequencies and percentages by system organ class and preferred term, severity, and relationship to study CTM for each treatment group. In summaries of TEAEs by severity and relationship to CTM for subjects reporting multiple episodes, all reported events will be included, not only the worst reported case. Serious Adverse Events will also be presented by relationship to the CTM.

The number of subjects with at least one AE will be tabulated for each treatment group. Differences between the treatment groups will be tested using Fisher's exact test. Then the number of AEs for each treatment group will also be tabulated.

The number of subjects and the number of AEs will be tabulated by severity, relationship, and local injection site specific events versus non local events.

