11.3 Relationship

The Relationship between an AE and the CTM will be determined by the Investigator on the basis of his or her clinical judgment and the following definitions:

Definitely Related: The AE follows a reasonable temporal sequence from administration of the CTM; the AE follows a known or expected response pattern to the CTM.

Probably Related: The AE follows a reasonable temporal sequence from administration of the CTM; the AE follows a known or expected response pattern to the CTM; and the AE could not be reasonably explained by the known characteristics of the subject's clinical state.

Possibly Related: The AE follows a reasonable temporal sequence from administration of the CTM; the AE follows a known or expected response pattern to the CTM, but could readily have been produced by a number of other factors.

Unlikely Related: The AE which etiology is unlikely related to the CTM even if event may follow a known or expected response pattern to the CTM, and likely to be produced by a number of other factors. Sufficient information is not available at the time of the AE to determine its causality.

Not Related: An AE for which sufficient information exists to indicate that the etiology is unrelated to the CTM. One or more of the following variables apply:

- The AE does not follow a reasonable temporal sequence following administration of the CTM;
- The AE is readily explained by the subject's clinical state or other therapies.

For events that are determined to be definitely, probably or possibly related, additional information on the relationship and timing of the event in relation to the arthrocentesis and study injection will be captured.

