11.5 Reporting

11.5.1 Adverse Events

All AEs that occur after signing the ICF will be recorded. At each visit during the trial, AEs that have occurred since the previous visit must be recorded. All subjects will be questioned and evaluated for

AEs or complications associated with the procedure. Complications of the injection include, but are not necessarily limited to: pain, swelling and/or inflammation at the injection site. The Investigator will determine the severity and relationship of each event, as defined above.

AEs observed during the course of this study, regardless of severity or relationship to the injection will be recorded on the appropriate eCRF. Each reported complication/AE will also include the duration, action taken to address the AE, and the resolution status (e.g. ongoing, resolved). These subjects will continue to be evaluated for safety and efficacy at all scheduled follow-up points.

The sponsor must report the results of an evaluation of an unanticipated adverse device effect (UADE) to relevant regulatory agencies and all reviewing ECs and investigators within timelines required by the regulatory agencies.

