14.2.2 Anticipated Adverse Reactions

Reported adverse reactions associated with the IA use of hyaluronic acid:

Intra-articular injection of sodium hyaluronate preparations has occasionally been associated with allergic/anaphylactic reactions and transient hypotension, which have generally resolved spontaneously or after conservative treatment.

The most common reported adverse events associated with Monovisc are the following: arthralgia, joint swelling and injection site pain.

Incidences of rash, headache, dizziness, chills, hives, itching, nausea, muscle cramps, peripheral edema, and malaise have also been reported in association with intra-articular injections.

A study conducted by Anika Therapeutics, Inc. on Monovisc recorded information on AEs that were possibly, probably and definitely related to the study injection. Patients who received Monovisc had 7.1% of AEs related to the study injection and 5.4% of patients who received saline had an AE related to the study injection. Most of the AEs were minor complications that required little or no treatment. These included injection site events, joint swelling, joint pain, and limb pain. The rate of joint pain and limb pain not related to the study injection was higher than the rate related to the study injection [26].

Reported adverse reactions associated with the IA use of corticosteroids:

Dermatologic: Whitening of the skin at the injection site, local fat atrophy.

Musculoskeletal: Joint infection, joint swelling and pain several hours after injection, tendon rupture, pain, swelling, ligament damage.

Neurological: Nerve damage.

General: Infection, local bleeding, allergic reactions.

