3.4 SAFETY ENDPOINT

The incidence, timing, severity, and relationship to treatment of all Adverse Events (AE) will be collected and coded using Medical Dictionary for Regulatory Activities (MedDRA). Local injection site and non-local events will be recorded separately.

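### Treatment-emergent is defined as treatment-related, so the only by-type adverse event table leaves out every event rated unlikely or not related

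*SAP*

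**What the plan says.** SAP 4.4 and Protocol 12.4 use the same definition: TEAEs are events "which are defined as AEs with an Investigator assessment of definitely, probably, or possibly related to CTM". Neither section gives an onset criterion. Both then specify that "TEAEs will be summarized with frequencies and percentages by system organ class and preferred term", and also by severity and relationship, for each arm.

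The same sections call for several displays of all AEs:

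- subjects with at least one AE, compared by Fisher's exact test;
- the number of AEs per arm;
- counts of subjects and events by severity, by relationship, and by local versus non-local.

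For serious events the SAP says: "Serious Adverse Events will also be presented by relationship to the CTM".

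The safety endpoint is wider than the TEAE set. SAP 3.4 states: "The incidence, timing, severity, and relationship to treatment of all Adverse Events (AE) will be collected and coded". Protocol 7.4 says the same. Protocol 11.3 defines five relationship levels: definitely, probably, possibly, unlikely and not related. On who assigns the level, Protocol 11.5.1 states: "The Investigator will determine the severity and relationship of each event".

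**The concern.** A treatment-emergent event is ordinarily one that begins or worsens after treatment, whatever its cause. Here the term selects on cause and ignores timing. Someone given the TEAE table would probably read it as all-cause, when it holds only what the Investigator attributed to the injection. If one arm had an excess of a particular event type and most of those events were rated unrelated, no class or term table would show it. Comparing arms by event type without regard to attribution is how a randomised trial can reveal such an excess.

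Two features of this study add to the problem.

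- **Late events.** The extension's own contribution is events 26 to 39 weeks after a single injection. Every related category in Protocol 11.3 requires a plausible time sequence from administration, and one listed ground for a rating of not related is: "The AE does not follow a reasonable temporal sequence following administration of the CTM". Late events are therefore the likeliest to be filtered out. This is an inference, because the documents give no rates by period.
- **Who rates.** The rating belongs to the Investigator. The PI is most often the Treating Physician, who is not blinded (Protocol 8.2 and 10.2.17). Entry to the only by-type table can therefore depend on an unblinded judgement.

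**Working it through.** The point rests on a definition and a list of specified tables, and the plan gives no figure to reproduce. The first step is to see which display shows which events.

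| Display in SAP 4.4 | Unlikely and not-related events included? | By class and preferred term? |
|---|---|---|
| TEAEs | No | Yes |
| Subjects with at least one AE (Fisher) | Yes | No |
| Number of AEs | Yes | No |
| By severity, relationship, local/non-local | Yes | No |
| SAEs by relationship | Yes, if serious | Not stated |

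No row is specified to have both properties. The by-type table covers 3 of 5 relationship levels. The text for the unlikely category also contains this sentence: "Sufficient information is not available at the time of the AE to determine its causality". Some omitted events may therefore be ones whose cause was simply undetermined. Of the all-AE displays, only the local/non-local split says anything about event type, and only coarsely. SAP 1.0 mentions listings, but a listing is not a by-arm summary.

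**Possible size.** Protocol 14.2.2 describes a saline-controlled Monovisc study in which related meant possibly, probably or definitely related, the same filter as here. It reports: "The rate of joint pain and limb pain not related to the study injection was higher than the rate related to the study injection". No figures are given for that split.

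Let s be the share of these pain events that are rated related, s = related / (related + unrelated). With unrelated greater than related, s < 0.5. With n subjects in an arm, all-cause incidence p and one event per subject, the number shown is below 0.5 × p × n and the number omitted is above it. Planned arm sizes are 256 Cingal and 64 TH (Protocol 12.1). The values of p are assumed.

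| p (assumed) | Cingal: 0.5 × p × 256 | TH: 0.5 × p × 64 |
|---|---|---|
| 5% | 6.4 | 1.6 |
| 10% | 12.8 | 3.2 |
| 20% | 25.6 | 6.4 |

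**Extension window.** 39 − 26 = 13 weeks, and 13/39 = 33% of follow-up. In days, 26 × 7 = 182 and 39 × 7 = 273, so the window is 91 days long and begins 182 days after injection. This measures follow-up time, not the number of events missed.

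**The case against.** The strongest reply is that nothing is hidden or lost. Both documents state the definition openly and in the same words. Every AE is recorded and MedDRA-coded, the all-AE tables count unrelated events, and the text says safety assessments will include TEAEs, which does not rule out other tables. That is all true, and it means the gap must not be described as unrelated events going unreported. But a table that is merely permitted is not prespecified, and none of those specified shows unrelated events by class or term.

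On blinding, the Blinded Evaluator collects and records AEs (Protocol 8.2) and carries out the week 39 assessments, including AEs (Protocol 10.4). This protects ascertainment. It does not move the relationship rating, which Protocol 11.3 and 11.5.1 give to the Investigator. Exposure to unblinded judgement is possible but not shown to occur, and it cannot be sized.

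The criticism of the sizing largely stands. The Monovisc statement compares rates without giving them, so the step to fewer than half needs the one-event-per-subject assumption. The incidences are illustrative. The arm sizes are planned numbers for the parent trial, and joining the extension is optional, so they do not describe weeks 26 to 39. The time-sequence criterion has no stated limit, which leaves the late-event argument an inference. The sentence on insufficient information follows one saying that other causes are likely, so how many undetermined events fall in that category is unclear. None of this is needed for the main point.

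**Conclusion.** The concern holds. Followed as written, the plan yields a table labelled TEAE that contains only Investigator-attributed events, and it specifies no by-arm summary by class and term for the other two relationship levels, although the safety endpoint covers all AEs. This follows from the text alone.

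The size is indicative. If the Monovisc-study pattern carries over to Cingal and TH, and each affected subject has one event, the table shows fewer than half of joint-pain and limb-pain events. The related shares for Cingal and TH are not given, so the carry-over is an assumption.

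The any-AE Fisher test and all efficacy analyses are unaffected by the rating. This is a change the sponsor should make to obtain complete and correctly labelled safety reporting. It does not threaten the efficacy conclusions.

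**What to change.** In SAP 4.4 and Protocol 12.4:

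1. Define a TEAE as any AE with onset or worsening on or after the Cingal 16-02 injection and through week 39, regardless of relationship.
2. Tabulate all TEAEs by system organ class, preferred term and severity for each arm.
3. Keep the currently defined set as a subset labelled treatment-related TEAEs.

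The cost is wording in both documents and one additional table. All AEs are already coded and their timing is already collected, so no event is re-rated and the onset criterion needs no new data. The SAP should say how worsening is identified from the recorded fields, because Protocol 11.5.1 does not list a date of worsening.

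The protocol wording requires an amendment with ethics committee approval and, as required, regulatory approval (Protocol 16.4). Adding an all-AE class and term table to the SAP alone would close the main gap sooner without contradicting the protocol, but the misleading label would remain until the amendment.

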10.2 Procedure Description

10.2.1 Informed Consent Form (ICF)

The subject will be asked to sign the ICF prior to attending the 39 week follow up visit.

All data collected in the clinical trial Cingal 16-02 will be utilized in Cingal 17-02. The demographics and assessments conducted at screening and baseline for Cingal 16-02 will be utilized as the demographic and baseline data for Cingal 17-02.

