4.1.1 Sample Size

The primary comparison in the study will be between Cingal and triamcinolone hexacetonide with respect to the difference in the change in the WOMAC pain score from baseline at 26 weeks after study injection.

It is assumed that the difference in the mean responses for Cingal and triamcinolone hexacetonide at 26 weeks would be 10 mm based on previous clinical trials of similar viscosupplementation products and the Cingal 13-01 trial with a standard deviation of 20. The sample size calculation is based upon a t-test. The sample size that is necessary to detect that specified difference at a power of 90% with a significance level of 5% in a 2:1 enrollment ratio is 128 in the Cingal group and 64 in the triamcinolone hexacetonide group. If a 15% drop out rate is assumed then enrolling in a 24:4:1 (Cingal: Monovisc :triamcinolone hexacetonide ratio) a total of 576 evaluable subjects, 256 subjects in the Cingal arm, 256 subjects in the Monovisc arm and 64 subjects in the triamcinolone hexacetonide arm is needed. This will provide 90% power to detect the difference between Cingal compared to triamcinolone hexacetonide at 26 weeks at a 5% significance level.

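### Adverse event timing is in the safety endpoint, but no planned AE table or test uses onset date and no AE window is stated, so the plan yields no estimate for the period after week 26

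*SAP*

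**What the plan says.** SAP 3.4 and Protocol 7.4 define the safety endpoint: "The incidence, timing, severity, and relationship to treatment of all Adverse Events (AE) will be collected". For events in the three categories of its scale that count as related (all except the unlikely and unrelated ones), Protocol 11.3 adds this: "additional information on the relationship and timing of the event in relation to the arthrocentesis and study injection will be captured".

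The analysis is in SAP 4.4 and, in matching terms, Protocol 12.4. Treatment-emergent events are defined by the investigator's relatedness call, with no reference to onset. They are summarised by system organ class, preferred term, severity and relationship. All AEs are tabulated by severity, relationship and local versus non-local. The between-arm comparison is on subjects affected: "The number of subjects with at least one AE will be tabulated for each treatment group". SAP 4.4 then says "Differences between the treatment groups will be tested using" Fisher's exact test. SAP 4.2 sets the 5% level.

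Four other places bear on which events are counted:
- Protocol 10.2.1: "All data collected in the clinical trial Cingal 16-02 will be utilized in Cingal 17-02".
- SAP 4.5: safety analyses cover every treated subject in any arm.
- Protocol 11.5.1: AEs are recorded from signature of the consent form, without saying whether the 16-02 or the 17-02 form is meant.
- Protocol synopsis (Sample Size): entering 17-02 is optional for those who completed week 26.

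**The concern.** The endpoint names four attributes: incidence, timing, severity and relationship. Three receive a table; timing receives none. There is no onset interval, no time-to-onset summary and no period-specific rate.

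This matters more here than in a stand-alone trial. No injection is given in 17-02. It adds about 13 weeks to a 26-week parent study, and its objective includes safety at 39 weeks. Its only new safety information is what happens after week 26. A single cumulative comparison would give no estimate for that period. A subject already counted for an early event, which may include the reactions Protocol 14.2.2 lists for intra-articular steroids ("Joint infection, joint swelling and pain several hours after injection, tendon rupture, pain, swelling, ligament damage"), could not contribute a later event to the Fisher test. An excess in one arm after week 26 would be diluted, and the 39-week result could largely repeat the 26-week one.

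**Working it through.** **What the plan's figures cover.** The documents give no AE rate and no power for any AE comparison. Their only sizing figure is for efficacy: "power of 90% with a significance level of 5% in a 2:1 enrollment ratio is 128 in the Cingal group and 64" for TH. With a 10 mm difference and SD 20, n(TH) = (1 + 1/2) × (1.960 + 1.282)² × (20/10)² = 1.5 × 10.51 × 4 = 63.1, so 64 TH and 128 Cingal. That reproduces, but says nothing about AEs. From here I use only the randomised arm sizes, 256 Cingal and 64 TH.

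**Step 1: endpoint against analysis.**

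| Attribute in SAP 3.4 / Protocol 7.4 | Analysis in SAP 4.4 / Protocol 12.4 |
|---|---|
| Incidence | Subjects with an AE, number of AEs, Fisher's exact test |
| Severity | Tabulated |
| Relationship | Tabulated |
| Timing | None |

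**Step 2: which window?** There are two readings, and each has a problem.

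- *Window from 16-02.* Protocol 10.2.1 and SAP 4.5 favour this. The comparison is then cumulative to week 39. If counting starts at the 16-02 consent, it also takes in the 7–14 day screening period before injection (Protocol 10.1), because the at-least-one-AE count has no onset condition.
- *Window from the 17-02 consent.* Protocol 11.5.1 permits this, and Protocol 10.3 lists AE assessment at the 17-02 Screening Visit. The all-treated denominator in SAP 4.5 then includes subjects never followed after week 26. If, as an assumption, 60% of each arm enters, true late rates of 20% and 5% appear as 0.60 × 20% = 12% and 0.60 × 5% = 3%. A 15-point difference shows as 9 points.

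**Step 3: size of the dilution on the cumulative reading.** All rates are assumptions: equal early rates e in both arms, late AEs 20% Cingal v 5% TH and independent of early ones, everyone in the extension, and a pairwise two-sided Fisher test at 5%.

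Cumulative share = e + (1 − e) × late rate. For e = 40%: 0.40 + 0.60 × 0.20 = 52%, and 0.40 + 0.60 × 0.05 = 43%.

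Exact power at 256 v 64:

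| Early rate, both arms | Cumulative shares | Power, cumulative | Power, late window |
|---|---|---|---|
| 20% | 36% v 24% | 42% | 89% |
| 30% | 44% v 33.5% | 32% | 89% |
| 40% | 52% v 43% | 23% | 89% |
| 50% | 60% v 52.5% | 18% | 89% |
| 60% | 68% v 62% | 13% | 89% |

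**Step 4: less favourable assumptions.**

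| Scenario | Power, late window | Power, cumulative |
|---|---|---|
| 20% v 5%, 60% take part (154 v 38) | 66% | 18%, 11%, 7% (e = 20%, 40%, 60%) |
| 15% v 5%, all take part | 58% | 21%, 12%, 8% (e = 20%, 40%, 60%) |
| 15% v 5%, 60% take part | 31% | 10%, 7%, 6% (e = 20%, 40%, 60%) |
| 10% v 5%, all take part | 17% | not computed |
| 10% v 5%, 60% take part | 9% | not computed |
| 20% v 5%, all take part, early rates 45% v 35% | 89% | 70% (56% v 38.25%) |

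The last row shows that, if early rates differ in the same direction, the cumulative test loses much less.

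**The case against.** The strongest reply has five parts.

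- **Pooling is inferred.** No passage states the AE window, and the consent wording in Protocol 11.5.1 could mean the 17-02 form. This stands: cumulative pooling is the natural reading, not a stated fact. It does not remove the need for action, because the other reading has its own denominator problem.
- **Late events are not invisible.** A reader might infer that a late difference would be hidden altogether. The documents do not support that. SAP 4.4 also counts AEs per arm, and its severity and relationship summaries include every reported event, so later events in subjects with an early AE still enter those counts. SAP 1.0 also mentions listings, whose content is not specified. What remains true is that the subject-level test cannot use those events, and neither counts nor listings give a between-arm estimate for the period.
- **Cumulative incidence is a legitimate answer.** Safety at 39 weeks after one injection can be read as everything from injection to week 39. No passage sets a week 26–39 comparison as an objective, and the endpoint sentence says timing is collected, not compared. This stands, and is why the cumulative table should be kept.
- **The power illustration is favourable.** A fourfold late excess, equal early rates and full participation all flatter the late window. SAP 4.4 also names no pairwise test for its three arms. This stands; step 4 of the working gives the range.
- **The late-window set is selected.** It holds those who completed week 26 and opted in, a subset formed after randomisation. This stands as a limit on the remedy.

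Nor does anything in the documents show that early events would dominate: Protocol 14.2.2 lists steroid reactions without rates by period.

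**Conclusion.** The gap is established from the text: timing is in the safety endpoint, no planned AE table or test uses onset, and the AE window is unstated in both documents. On the natural, cumulative reading, a difference arising after week 26 would be diluted in the only between-arm test, and no estimate for the extension period would be produced. On the alternative reading, late rates are understated by the share of treated subjects not followed.

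The size cannot be fixed from the documents because they contain no AE rates. For an assumed late 20% v 5% with equal early rates and full participation, power falls from 89% to between 42% and 13%. With other assumptions the loss is smaller, or the late window is itself too weak to detect much. These figures illustrate the mechanism; they are not a forecast. This is a worthwhile, low-cost improvement to the safety reporting, and it leaves the efficacy analysis untouched.

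**What to change.** In SAP 4.4 and Protocol 12.4:

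1. State the AE window, including which consent form starts recording and which events enter the 17-02 tables.
2. Exclude events with onset before the injection from the between-arm AE comparison.
3. Present the AE tables, including local versus non-local, by onset window: injection to week 26, and after week 26 to week 39. Use the subjects observed in each window as the denominator.
4. Give between-arm risk differences with 95% CIs for each window, labelled descriptive.
5. Keep the cumulative table on all treated subjects.

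The cost is SAP and protocol wording, repeat runs of the existing table programs using AE onset dates, and more tables to read. No new visits or assessments are needed. The late-window results will be imprecise, with at most 64 TH subjects, and come from an opt-in, post-randomisation subset. The report should say so beside the table, and should not read a wide interval as evidence of no difference.
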